A food frequency questionnaire (see appendix – *Microba* online questionnaire) will be collected at baseline and at 6 weeks (completed at testing visit 1). Analysis will be completed by *Microba (Australia)*. To control for diet and to assess whether there is an interaction between dietary inulin and supplement inulin, a 24-hour diet recall at baseline and post intervention (see appendix) will be collected during the second testing visit using the (The Automated Self-Administered 24-hour (ASA24) Dietary Assessment Tool developed by the National Cancer Institute (NCI)). This will be analysed using Food Works, Xyris, Australia (a nutrient analysis software).

Body composition

Body composition will be measured at baseline and 6 weeks. Measurements will include height, weight, waist and hip measurements. Circumferences will be calculated to the nearest 0.1 decimal using a measuring tape. Weight will be measured to the nearest 0.1 decimal using calibrated scales. Body fat will be measured via a Dual-energy X-ray Absorptiometry – DXA scan (Hologic QDR Series, Massachusetts, USA). The participant will be required to lay still in a supine position for approximately seven minutes.

Blood chemistry

A person trained in phlebotomy will take blood at baseline and 6 weeks. A small sample of venous blood will be collected from the superficial antecubital vein using 2 x 10ml vacutainers (red and purple vacutainers). The purple vacutainers (used for measuring whole blood and contain EDTA) will be placed on ice. The red vacutainers (contains no anticoagulant and used for serum) will remain at room temperature for 30 minutes. Before centrifuging, 3 x 300ul of whole blood will be collected for back up and placed in the freezer at -80 degrees Celsius. Remaining samples will be centrifuged at 1500G for 10 minutes at 4 degrees Celsius. Plasma and serum will be placed into 300ul aliquots and stored at -80degrees Celsius until analysis. Analysis of total cholesterol, HDL, LDL, triglycerides and glucose will be measured on an automated clinical chemistry analyser (Randox Datomer Plus) using the manufacturer's procedures.

Family and personal medical history

An adult pre-exercise screening tool will be completed prior to the intervention. *Microba* will also be measuring mental health and wellbeing using The Center for Epidemiologic Studies Depression Scale (CEDDS), day of sampling history, exercise and medical history pre and post intervention.

The following table outlines the information to be collected.

Measure	Pre	Post
Cardiorespiratory Fitness		
VO _{2peak}	X	X
Resting blood pressure	X	X
Resting heart rate	X	X
Maximum heart rate	X	X
Gene Predictor Score		
Total number of variants that contribute to high or low response to training		
Diet History		
Food frequency questionnaire	X	X
24-hour diet recall	X	X
Gut Microbiota		
Diversity	X	X
Short chain fatty acid	X	X
Body Composition		
Weight	X	X

Body mass index	X	X
Waist circumference	X	X
Body fat percentage	X	X
Blood chemistry		
Total Cholesterol	X	X
HDL	X	X
LDL	X	X
Triglycerides	X	X
Glucose	X	X
DNA	X	
Family and Personal Medical History		
Family History of Cardiovascular Disease	X	
History of Illness or Injury	X	
Smoking status	X	
Medications	X	
Exercise habits	X	
CESD-R score	X	X

Statistical Analysis

Determining the association between the gene predictor score and the gut microbiome

Following on from the GWAS, a genetic predisposition score for each participant will be calculated to test for the cumulative effect of multiple alleles on $\dot{V}O_{2peak}$ training response and cardiovascular disease risk factors. Using the genetic variants identified from our PREDICT HIIT study (results yet to be published) and taking the approach used in Thomaes et al. (2011), '0' will be given for a homozygote for alleles associated with a low response to training, '1' for heterozygote for an allele associated with high response, and '2' for homozygotes of an allele associated with high response to training. The $\dot{V}O_{2max}$ scores and other covariates will be collated for each participant. Microba will provide gut bioinformatics for each participant (pre and post intervention). The butyrate production per participant will also be calculated as described above (pre and post intervention). This information (including average fibre intake per participant) will be analysed using SPSS statistical software (IBM SPSS Statistics).

Data will be tested for normality using a Shapiro-Wilk test. Where normality is not found, the Kruskal-Wallis test will be used for comparing between data sets.

To compare the mean OTUs (and other bioinformatics provided by 'Microba'), fibre intake and butyrate production for predicted low and high responders (e.g. gene predictor score), a one-way analysis of co-variance (ANCOVA) will be calculated (with age and sex as covariates).

Investigating whether altering the gut microbiome via diet and training influences the $\dot{V}O_{2max}$ training response to HIIT

The change in $\dot{V}O_{2max}$ of each participant will be calculated. Low responders will be classified by a $\dot{V}O_{2peak}$ change of <100ml of O_2 /min, and high responders by a $\dot{V}O_{2peak}$ change of > 700ml in O_2 /min (following the intervention period).

To compare the mean change in OTUs, alpha diversity, fibre intake and butyrate production to $\dot{V}O_{2max}$ training response, a one-way analysis of co-variance (ANCOVA) will be calculated (with age, sex, baseline $\dot{V}O_{2max}$ as covariates).

A multiple regression analysis will be used to evaluate the role of possible predictors for change in $\dot{V}O_{2max}$. Predictors will be screened using a Spearman correlation matrix to find the top four significant variables to include in the multiple regression analysis (e.g. gene predictor score, sex, age, gender, BMI, fibre intake, OTUs, butyrate production, alpha diversity).

The above approach will also be used to compare changes in other biomarkers (e.g. blood tests, body fat percentage etc).

All statistical tests will be performed at a 5% significance level.

1. Montero, D. and C. Lundby, *Refuting the myth of non-response to exercise training: 'non-responders' do respond to higher dose of training*. JAP, 2017.
2. Mann, T., R. Lamberts, and M. Lambert, *High responders and low responders: factors associated with individual variation in response to standardized training*. Sports Med, 2014. **44**(8): p. 1113-1124.
3. Bouchard, C., et al., *Personalized preventive medicine: genetics and the response to regular exercise in preventive interventions*. Prog Cardiovasc Dis, 2015. **57**(4): p. 337-46.
4. Rankinen, T. and C. Bouchard, *Genetic predictors of exercise training response*. Current Cardiovascular Risk Reports, 2011. **5**(4): p. 368-372.
6. Williams, C., et al., *Genes to predict VO2max trainability: a systematic review*. BMC Genomics, 2017. **18**(Suppl 8:831).
7. Astorino, T. and M. Schubert, *Individual responses to completion of short-term and chronic interval training: a retrospective study*. PLoS One, 2014. **9**(5): p. e97638.

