The gut has received much attention over the past few years for its increasing role in human health and disease. Recent research has found a correlation between host genetics and the gut genome [8-10]; with $\dot{V}O_{2peak}$ associated with greater gut microbial diversity [11-14]. Gut microbiome diversity is a marker of health and can be increased by the consumption of prebiotic fibre [15-18].

There has been minimal, if any, research to identify the association between the gut microbiome and its effect on $\dot{V}O_{2peak}$ trainability. More specifically, do individuals with a low or high response genetic profile for trainability have differing gut microbiota; and can this microbiome be positively influenced to elicit greater CRF changes for the host?

The overall objective of IMPROVE HIIT is to contribute to evidence-based personalised medicine. Understanding the factors that influence training variability could be used to improve individualised exercise prescription, thereby contributing to health maintenance and treatment/prevention of disease.

AIMS

Primary Aim

- To identify if altering the gut microbiome with prebiotic supplementation influences the $\dot{V}O_{2max}$ training response to HIIT

Primary Hypothesis

- Altering the gut microbiome will influence the $\dot{V}O_{2max}$ training response to HIIT

Secondary Aims

- To identify if the gut microbiome is correlated to the gene predictor score
- To detect if altering the gut microbiome improves chronic disease risk factors

Secondary Hypotheses

- Gene predictor scores associated with the HIIT-induced $\dot{V}O_{2max}$ training response will be correlated with a specific gut microbiota taxa.
- Manipulating the gut microbiome will improve chronic disease risk factors
- The gene predictor score will predict lower vs higher responders to the HIIT-induced $\dot{V}O_{2max}$ response

BACKGROUND

The worldwide prevalence of chronic diseases, such as cardiovascular disease, cancers, stroke and diabetes is rising [19]. Low cardiorespiratory fitness is strongly associated with chronic diseases and premature mortality [20-22]. To alleviate the health and economic burden associated with low cardiorespiratory fitness, health guidelines across the world recommend individuals undertake regular exercise training [19].

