Improvements in cardiorespiratory fitness in response to exercise training varies greatly between individuals, with some people responding well or very well ('responders' or 'high-responders') to exercise training, whereas others only have mild increases in their cardiorespiratory fitness following similar exercise training ('low-responders') [2-4, 23, 24]. The ability to change cardiorespiratory fitness is a multifactorial trait [2, 4]. Considering cardiorespiratory fitness is one of the best integrative predictors of morbidity and mortality risk, it is important to understand how factors, such as genetics and environmental influences (e.g. training and diet), may predict the variability in response to exercise training. This knowledge could lead to targeted personalised exercise therapy to decrease the burden of chronic disease.

Predictor genes for $\dot{V}O_{2\max}$ trainability

From our systematic review, 35 studies identified 97 genes that predict $\dot{V}O_{2\max}$ trainability [6]. Exercise-related phenotypes are complex traits and are polygenic (i.e. influenced by many genes working together) with each genetic variant likely to be contributing a small percentage (typically less than 1%) to the overall change in $\dot{V}O_{2\max}$.

Approximately, 50% of the variance in $\dot{V}O_{2\max}$ trainability can be attributed to genetic make-up. A gene predictor score (GPS) based on these variants can predict who may be a lower or higher responder to training. A score of '0' represents homozygote (two copies of the same allele) for the low-response variant; '1' represents heterozygous (two different alleles, with one a high response allele) and '2' represents homozygous for the high-response allele. Individuals with a low score (e.g. <9 high response alleles) may be a lower responder to training.

Possible Gene Expression Mediators

Training intervention

HIIT has a lower frequency of 'non-responders' [7]; and greater improvements in vascular function, cardiorespiratory fitness and other biomarkers compared to other forms of training [7, 25]. This training requires individuals to exercise at a high intensity (e.g. 90% of maximum heart rate) for a specific period of time (e.g. 4 minutes) with a rest/recovery period (e.g. 3 minutes) in between [26].

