All non-coded records will be stored in a locked filing cabinet with restricted access for a minimum of five years in a private office of [name]. Any information obtained for the purpose of this research project that can identify a participant will be treated as confidential and securely stored. All computer records will be stored on an access-restricted and file-encrypted network (UQ's Research Data Management System). Only the Principal Investigator and Co-Investigators will have access to project's documents. It will be disclosed only with permission, or as permitted by law.

Data Collection

Primary outcomes

A panel of genetic variants will be identified from a saliva sample collected at baseline via an Oragene collection kit. Saliva samples will be sent to the Translational Research Institute (TRI) for DNA extraction and GWAS analysis. The GWAS will target predictor genes identified from our PREDICT HIIT study.

GWAS analysis

a) DNA extraction from saliva

DNA will be extracted from the stabilised saliva samples using the QIASymphony (Qiagen) DNA MIDI Kit (Cat.no. 937255). The yield and purity will be measured using the Trinean DropSense-96 as per the manufacturer's instructions.

b) Genotyping

100ng of DNA will be genotyped on Illumina Infinium HumanCoreExome24v1.1 arrays as per manufacturer's instructions. The arrays will be scanned on an Illumina iScan system and the raw fluorescence intensity data normalized and clustered for each sample using Illumina Genome Studio (v. 2011.1). Genotypes will be called using the standard Illumina HumanCoreExome24v1.1 cluster file.

c) GWAS

The program PLINK will be used to convert the .ped and .map files into .fam, .bim and .bed files. To this data, clinical files (co-variables and phenotypes) will be added. Data is filtered via the following steps: 1) sample level (call rate, heterozygosity, relatedness, ancestry), 2) SNP level (call rate, minor allele frequency, HWE). Two new types of data will be created: 1) principal components for capturing population-substructure, and 2) genotypes of untyped SNPs (using sanger imputation server for the imputations with HRC r1.1 as reference). Logistic regression will be performed with 'N' PCA components (N is unknown until we do the experiments). SNP coordinates are from the Genome Reference Consortium GRCh37 (hg19) build. A Manhattan plot will be created to visualise the significant genetic markers and raw density plot will be examined manually.

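### The gene score–microbiome aim is worded as a correlation, but the test named for it cuts the score into low and high groups; a continuous score would use the 40 participants better

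*Protocol*

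**What the plan says.** **Aim.** Under Secondary Aims, the protocol wants "To identify if the gut microbiome is correlated to the gene predictor score". The first of the Secondary Hypotheses likewise expects scores to be correlated with gut taxa.

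**Test.** The first part of Statistical Analysis, on the gene score and the microbiome, compares means of OTUs, other microbiome measures, fibre intake and butyrate "for predicted low and high responders (e.g. gene predictor score), a one-way analysis of co-variance (ANCOVA) will be calculated", with age and sex as covariates. No other test of this association is named, and no boundary between low and high is given there.

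**Score.** Each variant scores 0, 1 or 2 according to the number of high-response alleles, and these are added. The Background section on predictor genes reports that "35 studies identified 97 genes that predict" trainability. It goes on to say "A gene predictor score (GPS) based on these variants can predict who may be a lower or higher responder to training", and adds "Individuals with a low score (e.g. <9 high response alleles) may be a lower responder to training". The score planned for the trial comes from another source. The genotyping section says "The GWAS will target predictor genes identified from our PREDICT HIIT study", and Statistical Analysis builds the score "Using the genetic variants identified from our PREDICT HIIT study (results yet to be published"). The number of those variants is not stated.

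**Other thresholds.** The limits of <100 and >700 ml of oxygen per minute in the second part of Statistical Analysis classify the observed change in VO2peak, not the gene score.

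**The concern.** A question about correlation between two numeric quantities is most directly tested with both kept numeric. Grouping treats everyone on one side of the cut as alike and discards the ordering within groups. In a trial of 40 that loss can decide whether a moderate association is detected.

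A two-group comparison also needs a boundary. The only one in the protocol is the allele count of 9 in the Background. The score is a sum over variants, so its range grows with the number of variants, and a fixed count means something different on each panel. If that example were carried into the analysis, the split could be reasonable or very lopsided, depending on a panel that the document does not describe. Participants are not selected on the score, so nothing else would balance the groups.

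**Working it through.** **1. The plan's own figure.** The sample-size section uses a test of R² increase with f² = 0.22, one tested predictor out of six, and a 5% level. With N = 39, the denominator df is 39 − 6 − 1 = 32, λ = 0.22 × 39 = 8.58 and the critical F is 4.149. The noncentral F gives power 0.8106, which matches the protocol. That calculation is for the regression model; the protocol gives no power figure for the gene score–microbiome aim.

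**2. Cost of cutting the score.** Inputs from the protocol: n = 40, two-sided 5%, age and sex as covariates. Assumptions: a normal score and a true correlation r, which the documents do not give.

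Cutting a normal score at quantile q multiplies the correlation by a = φ(z_q)/√(q(1−q)). The share of information kept is a².

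- Median split (q = 0.5): a = 0.798, a² = 0.64, equivalent to 0.64 × 40 ≈ 25 participants.
- 20/80 split (q = 0.2): a = 0.700, a² = 0.49, equivalent to about 20 participants.

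Power comes from the noncentral F with df 1 and 40 − 2 − 2 = 36, and λ = 40·r²/(1 − r²). The split uses a·r in place of r. Example at r = 0.4: λ = 40 × 0.16/0.84 = 7.62 gives power 0.77. After a median split, r becomes 0.319, λ = 4.54 and power is 0.55.

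| True r | Continuous score | Median split | 20/80 split |
|---|---|---|---|
| 0.30 | 0.49 | 0.33 | 0.26 |
| 0.40 | 0.77 | 0.55 | 0.43 |
| 0.45 | 0.87 | 0.66 | 0.53 |
| 0.50 | 0.94 | 0.76 | 0.63 |

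**3. Does an allele count carry over between panels?** With m independent variants and a common high-response allele frequency p (both assumed), the score is Binomial(2m, p). The expected share of people scoring below 9 is the distribution function at 8.

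| Variants m | p | Mean score 2mp | Share below 9 |
|---|---|---|---|
| 9 | 0.5 | 9.0 | 41% |
| 10 | 0.5 | 10.0 | 25% |
| 15 | 0.3 | 9.0 | 43% |
| 20 | 0.2 | 8.0 | 59% |
| 20 | 0.3 | 12.0 | 11% |
| 20 | 0.5 | 20.0 | 0.01% |
| 97 | 0.05 | 9.7 | 36% |
| 97 | 0.10 | 19.4 | 0.2% |
| 97 | 0.20 | 38.8 | about 1 in 10 billion |

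The same count gives a sensible split on some panels and no low group on others. Panel size and allele frequencies decide which, and the document gives neither for PREDICT HIIT.

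**The case against.** A reader might infer something stronger: that the cut-off of 9 cannot work, because on a 97-gene score almost nobody would fall below it and the low group would be empty. The document does not support this, for three reasons.

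- The sentence sits in the Background and is hedged as an example of who may respond less. Statistical Analysis states no gene-score cut-off, so a median or other relative split fits its wording equally well.
- The trial's score is not built on the 97 genes. Both the genotyping section and Statistical Analysis point to the PREDICT HIIT variants. The 97 is a count of genes from a review, and no 97-variant score is planned.
- On a short panel a count of 9 can divide people sensibly, as the 9- and 15-variant rows above show.

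The final variant list and the group boundary may also properly be left to a statistical analysis plan, so their absence is not counted here.

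There is also a case for grouping. The introduction asks whether people with low or high genetic profiles have different microbiota, which is a group question, and another secondary hypothesis concerns lower versus higher responders. That hypothesis is about VO2max response, though. The introductory question justifies showing group means; it does not make a cut the best test of a correlation. The multiple regression in the second part of Statistical Analysis lists the gene score as a candidate predictor without cutting it, but its outcome is change in VO2max (with the same approach extended to other biomarkers), so it does not test the score against the microbiome.

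Finally, the correlations and the 20/80 split are illustrations. That stands: the power figures show the scale of the loss and are not a forecast for this trial.

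**Conclusion.** The point holds as a mismatch between a secondary aim and its test. The aim and first secondary hypothesis are correlations; the single test named for them compares groups formed by cutting the score. If the score is roughly normal, the loss is at least 36% of the information, or about 15 of 40 participants' worth. At r = 0.4 to 0.45 that is about 21 to 22 points of power against a median split. The percentage does not depend on r, but the power figures do.

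The allele count of 9 is a lesser matter. It is an example not tied to the panel in use, and its suitability for that panel cannot be judged from the document, so it should not be relied on to form groups. Severity is minor: this is a secondary aim of a self-described pilot, and the change is a cheap improvement.

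**What to change.** In the first part of Statistical Analysis, make the main test of the gene score–microbiome aim a regression (or partial correlation) of each microbiome or butyrate measure on the continuous gene score, adjusted for age and sex as already planned. Express the score as high-response alleles divided by the number of variants typed, so that it does not depend on panel size.

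Keep the low/high comparison as a descriptive display, with the cut either fixed in advance from PREDICT HIIT or set at the sample median. In the Background, delete the example of 9 alleles or tie it to the PREDICT HIIT panel by stating that panel's number of variants and score range.

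The cost is wording only: no new data, visits or assays. The downside is that the low/high group means become descriptive rather than the formal test.

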Our gut microbiome is predetermined by host genetics that can be manipulated through numerous external factors, such as exercise and diet. Whilst host genetics and associated gut taxa increases susceptibility to various chronic diseases and overall fitness levels, the relationship between the gut microbiome and $\dot{V}O_{2max}$ trainability is unknown.

In addition to examining the gene predictor score for $\dot{V}O_{2max}$ trainability, our study will also investigate microbiota-related genes, host genes related to gut microbiome composition, and the genes involved with the gut-microbiota cross-talk. In conclusion, we hope to collect data to help understand if manipulation of the gut microbiome can improve the training response of individuals with a low gene predictor score for $\dot{V}O_{2max}$ trainability.

RESEARCH PLAN

Improving High Intensity Interval Training Response (IMPROVE-HIIT)

Overview

Improve HIIT will examine the association between the gene predictor score for $\dot{V}O_{2max}$ trainability the gut microbiome; and to investigate whether altering the gut microbiome via diet and training influences the $\dot{V}O_{2max}$ training response to HIIT.

Design

Improve HIIT is an 8-week randomised trial with two groups allocated to either: (1) HIIT plus placebo; or (2) HIIT plus prebiotic

Study Population

Consenting adults aged over 18 years.

Power Calculation (sample size justification)

The proposed project will be a pilot study. Considering financial resources, a sample size of 40 is possible. When using G*Power (download.cnet.com) ([52]), a sample size of 39 will achieve a medium effect size of 0.22 (using 6 predictors). This participant number is similar to a previous study examining if gut taxa is related to $\dot{V}O_{2max}$ levels [12]. A linear multiple regression model was used to include covariates that may contribute to the overall outcome (e.g. 6 predictors may include BMI, age, gender, initial $\dot{V}O_{2max}$, initial gut microbiome and cholesterol levels). Below are results of the power calculation:

F tests - Multiple Regression: Special (R^2 increase)

Analysis: A priori: Compute required sample size

Input:	Effect size f^2	= 0.22
	α err prob	= 0.05
	Power (1- β err prob)	= 0.8
	Numerator df	= 1
	Number of predictors	= 6
Output:	Noncentrality parameter λ	= 8.58
	Critical F	= 4.149097
	Denominator df	= 32
	Total sample size	= 39
	Actual power	= 0.8106

Recruitment

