Participants will be recruited through Exercise Physiology Brisbane channels (where principal investigator works) channels. These channels will include current patients, Facebook, emails, face-to-face, doctor's surgeries) using referrals, email, newsletters and snowballing (see appendix for wording). Additionally, an email will be sent out to current staff and students from the University of Queensland. This process will begin once ethics has been approved and continue until 40 people have been recruited (within a 12-month time-frame).

Inclusion Criteria

- Inactive adults aged between 18 and 50 years
- Less than 60 minutes of structured exercise each week
- Signed consent form

Exclusion Criteria

- Antibiotic use 6 months prior to intervention or antibiotic use during intervention.
- Pre- or-probiotic use within four weeks of participating in study
- Pregnancy, chronic infections, auto-immune diseases and intestinal chronic conditions (e.g. IBS, Crohn's disease, ulcerative colitis, coeliac disease).
- Existing cardiac conditions
- Recent surgery or orthopaedic conditions that prevents treadmill walking/running

- Diabetes
- Allergies to inulin (chicory root) or fructans
- Allergies to maltodextrin and other polysaccharides
- Allergies to soy, milk and egg (there maybe traces of these in maltodextrin)
- Greater than 60 minutes of exercise per week within four weeks of the study

Rationale for Criteria

Antibiotics can decrease gut microbiome diversity [35]. As such, participants on antibiotics up to 6 months prior to the study will be excluded. Moreover, pre-and probiotics may alter gut composition; participants on these supplements (up to four weeks prior) will be excluded. The age and exercise inclusion criteria have been added to create a more homogenous group. Other exclusions are included for participant safety (e.g. to avoid exacerbating existing conditions or placing the participant at a greater risk for a health complication).

Informed consent

Through the recruitment, information will include details about the study and the above-mentioned inclusion and exclusion criteria. The contact details for the Research Team will be provided.

Once participants have registered their interest and the Research Team check they meet the inclusion criteria, they will be asked to sign the informed consent form (via email or posted) and to come to the University of Queensland for the following baseline testing sessions.

Baseline testing sessions

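### The claim of 80% power for a medium effect does not describe the prebiotic-versus-placebo comparison: f² = 0.22 is about 0.94 residual SD between arms, and the arm is not named as the tested term

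*Protocol*

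**What the plan says.** The Primary Aim is to find out whether prebiotic supplementation influences the VO2max response to HIIT. The Design and Randomisation sections set this up as two arms, with 20 envelopes for each.

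The section Power Calculation (sample size justification) calls the trial a pilot, says that 40 is what resources permit, and then states that "a sample size of 39 will achieve a medium effect size of 0.22 (using 6 predictors". The G*Power block is headed "F tests - Multiple Regression: Special (R^2 increase". Its inputs are f² = 0.22, alpha 0.05, power 0.8, "Numerator df = 1" and six predictors. Its outputs are noncentrality 8.58, critical F 4.149097, denominator df 32, total N 39 and actual power 0.8106. The text illustrates the model with "6 predictors may include BMI, age, gender, initial" VO2max, initial gut microbiome and cholesterol. It does not say which predictor is tested.

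Recruitment is to "continue until 40 people have been recruited (within a 12-month time-frame". Under Withdrawal Criteria, the data of participants who withdraw are deleted. No allowance for loss is stated.

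Under Statistical Analysis, change in VO2max is regressed on predictors chosen by a Spearman screen to "find the top four significant variables to include in the multiple regression analysis". The examples listed there do not include the arm either.

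**The concern.** A reader will take the section to mean that the trial has 80% power to detect a moderate effect of the prebiotic. Two things stand in the way.

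- **Which hypothesis is powered.** With one numerator degree of freedom, the calculation concerns a single term. That term is not identified, and the six examples are all baseline characteristics. The sample size is also compared with that of a study relating gut taxa to VO2max levels, which is a question of association and not of a randomised effect.
- **How large the effect is.** No SD, target difference or earlier estimate supports 0.22, and it is not translated into a difference between arms. That translation shows how demanding the assumption is.

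At stake is the interpretation of the result. If the true effect is moderate, a non-significant result is the more likely outcome at this size, and the stated power would give no warning of that.

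**Working it through.** **Inputs.** From the power section: f² = 0.22, alpha 0.05, one tested term, p = 6 predictors, N = 39. From Randomisation: 20 per arm. From Recruitment: a maximum of 40. The loss rates of 10% and 20% used below are assumptions; the protocol gives none.

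**Step 1: reproduce the plan's figure.** For the R²-increase F test with one tested term:

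- λ = f² × N = 0.22 × 39 = 8.58
- denominator df = N − p − 1 = 39 − 6 − 1 = 32
- critical F(1, 32) at 5% = 4.1491
- power = P(noncentral F > 4.1491) = 0.8106

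Every output agrees with the protocol. N = 38 gives 0.7998, so 39 is the smallest N that strictly reaches 0.80.

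**Step 2: translate f² into a difference between arms.** Code two equal arms as ±½. The arm variable then has variance ¼. A difference of d residual SDs explains d²/4 in units of the residual variance, so f² = d²/4 and

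d = 2 × √0.22 = 0.938 residual SD.

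On the raw scale this is multiplied by √(1 − R²), where R² is the share of variance explained by the covariates:

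- assumed R² = 20%: 0.938 × √0.8 = 0.84 raw SD
- assumed R² = 50%: 0.938 × √0.5 = 0.66 raw SD

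**Step 3: power for smaller effects (N = 39, p = 6).**

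| Effect | Power at 39 | N for 80% |
|---|---|---|
| f² = 0.22 (0.94 residual SD) | 0.811 | 39 |
| f² = 0.15 (2√0.15 = 0.77 residual SD) | 0.650 | 55 |
| f² = 0.5²/4 = 0.0625 (0.5 residual SD) | 0.328 | 128 |

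**Step 4: loss (f² = 0.22, p = 6).**

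| Analysed | Power |
|---|---|
| 39 | 0.811 |
| 38 | 0.800 |
| 36 = 40 × 0.9 (assumed 10% loss) | 0.776 |
| 32 = 40 × 0.8 (assumed 20% loss) | 0.723 |

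**Step 5: the same for a model built on the arm.** Take arm plus baseline VO2peak, age and sex, so p = 4 and df = n − 5. The 95% CI half-width in residual SD is t(0.975, n − 5) × 2/√n.

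| Analysed | Detectable d at 80% power | Power at d = 0.5 | CI half-width |
|---|---|---|---|
| 40 | 0.91 | 0.337 | 2.030 × 2/√40 = 0.64 |
| 36 | 0.96 | 0.307 | 2.040 × 2/√36 = 0.68 |
| 32 | 1.03 | 0.276 | 2.052 × 2/√32 = 0.73 |

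**Step 6: does the number of predictors matter?** At N = 39 and f² = 0.22, power is 0.812 with four predictors, 0.811 with six and 0.810 with seven. It hardly moves.

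**The case against.** The best defence has four parts.

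- **It is a pilot, sized by budget.** This stands as a reason for 40 participants. It does not support attaching 80% power for a medium effect to that number.
- **The value 0.22 is printed with every input, so nobody is misled about it.** On the usual f² conventions (0.15 medium, 0.35 large; neither is in the protocol), 0.22 lies between the two and nearer to medium. That is fair on the f² scale. For a two-arm comparison, however, 0.94 residual SD exceeds the usual large value of 0.8. In raw SD it may be smaller, but even the assumed 50% explained variance leaves 0.66.
- **The predictor list is only illustrative.** This stands: the wording is *may include*, so the protocol does not rule the arm out. The point is that the tested term is unnamed and the six examples use all six places.
- **Adding the arm changes nothing numerically.** Also true (Step 6). The issue is which hypothesis the power refers to, not the sample size.

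A reader might also infer that the trial can afford to lose only one participant, since 39 are required and 40 recruited. The figures do not bear this out: 38 analysed still gives 0.80, and the decline becomes noticeable nearer 36. Nor does the change from six example predictors to four screened ones invalidate the power figure. Screening is a question about the analysis and has almost no effect on this calculation.

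**Conclusion.** The concern holds as a fault of interpretation and alignment, not of arithmetic. The calculation reproduces exactly. What is wrong is the claim drawn from it: 80% power for a medium effect is not tied to the randomised comparison, and for that comparison it means about 0.94 residual SD. Power at 39 analysed is 0.65 for f² = 0.15 and 0.33 for 0.5 residual SD. Loss is not allowed for, and at the assumed 10% and 20% power for f² = 0.22 falls to about 0.78 and 0.72.

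These figures assume equal arms, covariates unrelated to arm (as randomisation gives on average), and effects expressed in residual SD. The raw-scale values and the loss rates are assumptions.

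Two further inferences are not supported. The protocol does not say that a non-significant result will be read as no effect; the risk is that its power statement leaves that reading open. Nor does the shortfall show that more participants must be enrolled, since a pilot can be reported by its estimate and precision.

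**What to change.** Keep the enrolment target and rewrite the power paragraph.

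1. Delete *medium*.
2. Name randomised arm as the tested term, with baseline VO2peak, age and sex as covariates. The ANCOVA in Statistical Analysis already uses this set.
3. In the Statistical Analysis regression, keep arm in the model whatever the screening selects.
4. Replace the power claim with wording such as:

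> With 40 analysed, 80% power is available for a between-arm difference of about 0.91 residual SD; if 10–20% are lost (assumed; 36–32 analysed), about 0.96–1.03 residual SD. Power for 0.5 residual SD is about 34% at 40 and 31–28% at 36–32. As a pilot, the result is the estimate with its 95% CI (expected half-width about 0.64 residual SD at 40 analysed, 0.68–0.73 at 36–32); non-significance is not evidence of no effect.

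The cost is one rewritten paragraph and one added sentence in the analysis section, with no new participants, procedures or data. The drawback is that the stated figure becomes less favourable.
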